- The treatment history section of the Form 90 will be modified to be administered online at baseline and follow-up, to gather lifetime treatment history, self-help attendance, and treatment use.
- Readiness to Change. We will utilize the Readiness to Change Treatment Version (RCQTV), which RCQTV has been shown to have solid reliability and validity and has been modified for individuals contemplating or engaged in treatment for alcohol problems.

Follow-Up

The US AUDIT, TLFB, SIP-R, and Readiness to Change questionnaires will be used for the follow-up assessments. In addition, those in the app and chatbot groups will be asked to complete the System Usability Scale to assess their perceptions of the interventions' usability. The follow-up survey will be sent to participants at 4 months post-enrollment.

Interviews

Interviews will be conducted after the completion of the follow-up survey. Interview questionnaires will focus on users' experiences with the app or the chatbot. These interviews will be conducted over the phone.

8. Assessment of Safety

Several safety measures will be put in place to ensure the safety, comfort, and confidentiality of all participants. Care will be taken to inform potential participants fully before they consent to participate about all potential risks that may arise from their participation. The two most important aspects of participant protection in the proposed work are assuring the adequacy of informed consent (including full disclosure of all potential risks) and protecting confidentiality. To minimize risk, we will clearly explain all procedures to participants in our informed consent documents and clearly outline safeguards for confidentiality implemented in the study. Further, in order to protect their confidentiality, all participants will be encouraged to set a password to access their smartphone home screen.

Also, a Data Safety Monitoring Board (DSMB) will be convened in Year 1 of the project and will include the following two members with expertise in psychology, behavioral health, and

research ethics. The DSMB will meet twice during each year of the project to review the status of the project.

9. Statistical Considerations

All randomized study participants who complete both the baseline and follow-up surveys will be the primary population for the analysis. Three subgroups will be analyzed: the app group, the chatbot group, and the delay group.

Outcomes, Statistical Methods, and Statistical Analyses

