All outcomes will be presented using descriptive statistics. Binary and categorical variables will be presented using counts and percentages. SPSS 27 will be used for all statistical analyses.

Research Question 1: Do participants reduce their alcohol consumption more when using the app or the bot?

Hypothesis 1: Participants using either the app or bot will show a significantly greater reduction in alcohol consumption and alcohol related problems than participants in the delay group.

Method: Repeated Measures Anova

Baseline and Follow-up data from the Alcohol Use Disorder Identification Test (USAUDIT), Short Inventory of Problems-Revised (SIP-R), Readiness to Change Questionnaire (RTCQ), and Timeline Followback (TLFB) will be compared between app, chatbot, and delay groups. Consumption data used from the TLFB will include drinks per day, percentage of days abstinent, and heavy drinking days. Average drinks per day will be calculated from the reported last 14 days of drinks. Percentage of days abstinent will be calculated as the percentage of days in the recent 14 days that participants reported 0 drinks. Heavy drinking days will be calculated as the number of days in the past 14 days that participants report drinking more than 3 drinks if they are an assigned female at birth or 4 drinks if they are an assigned male at birth. Repeated measures ANOVA will be ran to identify if there is an interaction between time and group. An interaction would indicate a significant difference between app, bot, and delay groups in the difference of their baseline and follow-up drinking data.

Research Question 2: Do participants utilize the app and bot differently?

Hypothesis 2: Participants in the bot group will utilize the intervention significantly more than the app group due to the intervention's conversational interface.

Method: Independent sample t-test

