Utilization data will be collected from participants who use either the app or the chatbot. Three variables will be collected to measure utilization: total visits, duration of use, and total active days used. Total visits will be measured by the number of times a participant interacts with a feature of the app or the bot. Duration of use will be calculated as the amount of time in between a participants most recent visit to the app or bot and their date of installing the app or bot. Active days used will be calculated by the number of days a participant interacted with the app or bot. Utilization will be calculated for both app and bot users. Independent sample t-tests will be conducted between the means of each variable to determine if there were significant differences between app and bot users.

Research Question 3: Does utilization of the app or bot influence drinking outcomes?

Hypothesis 3: Utilization of the app or bot will mediate drinking outcomes, in that the higher the utilization of the intervention, the greater reduction of drinking the participant will have between baseline and follow-up

Method: Mediation analysis

Utilization data and TLFB data will be used in this analysis. A mediation analysis will be conducted with group as the independent variable, change in drinking as the dependent variable, and utilization as the mediator. Significant effects of usage on change in drinking will determine if utilization predicts change in drinking for either group. A significant indirect effect will determine if utilization mediates the relationship between group and outcome.

10. Ethics/Protection of Human Subjects

Ethical Standard

The investigator will ensure that this study is conducted in full conformity with Regulations for the Protection of Human Subjects of Research codified in 45 CFR Part 46, 21 CFR Part 50, 21 CFR Part 56, and/or the ICH E6.

Institutional Review Board

The protocol, informed consent form(s), recruitment materials, and all participant materials will be submitted to the IRB for review and approval. Approval of both the protocol and the consent form must be obtained before any participant is enrolled. Any amendment to the protocol will require review and approval by the IRB before the changes are implemented to the study. All changes to the consent form will be IRB approved; a determination will be made regarding whether previously consented participants need to be re-consented.

Informed Consent Process

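### Research Question 3 relates self-chosen use to drinking with no usage cut-off ahead of the outcome window and no readiness covariate, so it supports an association rather than influence

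*Combined protocol and SAP*

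**What the plan says.** **Question and model (section 9, Research Question 3).** The question is "Does utilization of the app or bot influence drinking outcomes". On inputs, the plan says "Utilization data and TLFB data will be used in this analysis", and the model is stated as "A mediation analysis will be conducted with group as the independent variable, change in drinking as the dependent variable, and utilization as the mediator". No covariate is named. The reading rule is "Significant effects of usage on change in drinking will determine if utilization predicts change in drinking for either group".

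**Use (section 9, Research Question 2).** Total visits and active days are counts with no time window. For the third measure, "Duration of use will be calculated as the amount of time in between a participants most recent visit to the app or bot" and the installation date. Section 7 has usage data uploaded continually and gives a minimum of three months of use, but no maximum.

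**Outcome.** Under Research Question 1, "Average drinks per day will be calculated from the reported last 14 days of drinks"; days abstinent and heavy drinking days use the same 14 days. Section 7, Follow-Up: "The follow-up survey will be sent to participants at 4 months post-enrollment".

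**Readiness.** Section 7 lists a readiness-to-change questionnaire at baseline. Section 9 uses it only as one of the measures compared between arms in Research Question 1.

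**The concern.** Randomization protects the comparison of arms. It does not protect the path from use to change in drinking, because use is the participant's own choice after randomization. Two features of the plan leave that path more exposed than it needs to be.

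- **Timing.** A mediator should come before its outcome. With no end date for use, activity inside the 14-day outcome window counts toward the mediator. Someone who is drinking less in those two weeks may open the app more often for that reason.
- **Common cause.** A participant who is more ready to change may both use the product more and drink less, even if use does nothing. The variable that would partly account for this is collected but not used.

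A significant path would be read as an answer to a question about influence. Phase III includes revising the intervention in the light of the findings, so a misread association could misdirect that work.

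**Working it through.** The plan gives no figure for Research Question 3, so there is none to reproduce. Inputs from the documents: at least 50 per arm (section 6, Target Sample Size), so n = 100 for app plus chatbot; follow-up at 4 months; a 14-day outcome window. Assumptions not in the documents: two-sided 5%, no true effect of use, baseline to follow-up correlation 0.5, and correlations of 0.1/0.2/0.3 for each mechanism.

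**1. Dates.** Four calendar months is 120 to 123 days. The outcome window therefore opens between day 120 − 14 = 106 and day 123 − 14 = 109 after enrollment. Day 105 is the last day sure to precede it. If counting stops at follow-up on day 120, 14/120 = 12% of the days lie inside the window; 12% is taken as the share of the variance of use.

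**2. Use that follows drinking.** Let late use be a share f of the variance of total use, correlate −c with change, and be unrelated to earlier use, which is itself unrelated to change. Total use then has correlation ρ = c√f with change (in size). The test of use, adjusted for group, has 97 degrees of freedom, critical value 1.985 and noncentrality δ = ρ√97 / √(1 − ρ²).

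| f | ρ at c = 0.1/0.2/0.3 | δ | Rejection, formula | Rejection, simulation |
|---|---|---|---|---|
| 0.12 (to follow-up) | 0.035/0.069/0.104 | 0.34/0.68/1.03 | 6.3/10.4/17.5% | about 6/11/17% |
| 0.25 (beyond follow-up) | 0.05/0.10/0.15 | 0.49/0.99/1.49 | 7.8/16.5/31.6% | 8/17/31% |

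On the same scale of days, a 25% share needs use counted for x days after follow-up, where (14 + x)/(120 + x) = 0.25, so x = 16/0.75 = about 21 days.

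**3. Readiness.** Let readiness correlate r with use and with follow-up drinking, and not with baseline drinking. In SD units the variance of change is 1 + 1 − 2 × 0.5 = 1, so use and change correlate r² = 0.01/0.04/0.09. Then δ = 0.10/0.39/0.89 and the rejection rate is 5.1/6.8/14.3%.

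**4. Fewer completers.** Section 9 analyses completers. At n = 70 the formula gives 5.9/8.7/13.5% for step 2 with f = 0.12, and about 5/6/11% for step 3.

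**5. Indirect effect.** By joint significance this also needs a significant group-to-use path, so its false rate is roughly the product of the two rates. With equal use in the arms, 17% × 5% = 0.9%. With an assumed 0.5 SD arm difference in use (71% power at 50 per arm), 17% × 71% = 12%. Hypothesis 2 expects such a difference: "Participants in the bot group will utilize the intervention significantly more than the app group".

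**6. Power cost of the fixes.** Assume a true slope of 0.3 SD per SD of use and residual SD 1. The plan's model has δ = 0.3√97 = 2.95, power 83%.
- Readiness covariate: δ = 0.3√(96(1 − r²)), where r is its correlation with use. From r = 0 to 0.3, power is about 82% falling to 79%.
- Cut-off, last 14 days effective, 12% of variance and unrelated to earlier use: δ = 0.3√(0.88 × 97) / √(1 + 0.09 × 0.12) = 2.76, power 78% (79% simulated). It is 80% or 82% if late use correlates 0.5 or 0.8 with earlier use.
- Cut-off, late use effective, 25% of variance and unrelated to earlier use: δ = 0.3√(0.75 × 97) / √(1 + 0.09 × 0.25) = 2.53, power 71%.
- Cut-off, late use pure noise at 25% of variance: power rises from 71% to 83%.

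**The case against.** **Counting naturally stops at follow-up.** The synopsis ends the primary protocol at completion of follow-up, sections 5 and 7 tie the period of use to the 4-month visit, and Hypothesis 3 concerns change between baseline and follow-up. This stands: a reader might infer that use after follow-up will be counted, but the documents show only that nothing excludes it. The 12% row is therefore the main case and the 25% row a less natural one. Stopping at follow-up still overlaps the whole 14-day outcome window.

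**The decision rule speaks of prediction.** This stands in part. Prediction is a fair description of the path, but the question it is meant to answer is about influence.

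**Readiness matters little.** At correlations of 0.1 or 0.2 the inflation is indeed trivial. The covariate is worth adding because it is already collected and costs little.

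**Late use may be active treatment.** It may, since daily assessment and weekly feedback continue. The cut-off then loses power, up to about 12 points in the least favorable case shown (83% to 71%). That is why use up to follow-up should be reported alongside it.

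**The change score is wrong.** A reader might infer this from regression to the mean. The documents do not support it: a change score fits Hypothesis 3, and any bias depends on a correlation between use and observed baseline drinking that is not given and could have either sign.

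**Conclusion.** The concern holds at low severity. Research Question 3 tests an unrandomized path, lets the mediator overlap its outcome window, and omits a collected baseline variable that plausibly affects both use and drinking. With n = 100 and the assumed correlations of 0.1/0.2/0.3, false rejection of the use-to-change test is about 6/11/17% from use in the last 14 days, more if use after follow-up is also counted, and about 5/7/14% from readiness. The existence of the gap is a matter of the text; its size rests on correlations that the documents do not give.

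Two stronger readings should be resisted. The first is that the trial's main results are compromised: the randomized comparisons and the rule in section 4 for choosing the next trial do not use this path. The second is that a cut-off and a covariate would return the test to 5%. That follows only if earlier use is unrelated to drinking and readiness is the sole common cause, measured without error. If use tracks drinking throughout the study, or other causes of use go unmeasured, bias remains.

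**What to change.** In section 9, Research Question 3:

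1. Count visits, active days and duration only up to a fixed day after enrollment that precedes the earliest opening of the follow-up TLFB window, no later than about day 105. Keep installation as the start of duration. Report use up to follow-up as a sensitivity analysis. Leave the Research Question 2 measures as defined, or state a cut-off for them too.
2. Add baseline (not follow-up) readiness to change as a covariate in both the mediator and the outcome model.
3. Keep the change-score model, and report a baseline-drinking-adjusted model as a sensitivity analysis only. Do not require both to be significant.
4. Report the use-to-drinking path as an association, and name reverse causation and unmeasured confounding as limits.
5. State that the analysis compares app with chatbot, or say how delay-arm use is handled. That arm receives the app after 3 months (section 4) and so may have about a month of use before follow-up.

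The cost is SAP wording; all the data are already collected. Under the assumptions above, the readiness covariate lowers power by about 1 to 4 points. The cut-off lowers it by about 1 to 5 points if use in the last 14 days really works, or by up to about 12 points if late use is 25% of the variance and unrelated to earlier use.

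### Research Question 3's single pooled use slope cannot show whether utilization predicts drinking change in each product, and its indirect effect answers a different question

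*Combined protocol and SAP*

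**What the plan says.** Hypothesis 3 (Section 9, Research Question 3) says that utilization mediates drinking outcomes, and spells this out as a dose-response: "the higher the utilization of the intervention, the greater reduction of drinking the participant will have between baseline and follow-up".

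The model is given in one sentence: "A mediation analysis will be conducted with group as the independent variable, change in drinking as the dependent variable, and utilization as the mediator". Two readings follow. The first concerns the usage effect: "Significant effects of usage on change in drinking will determine if utilization predicts change in drinking for either group". The second concerns the indirect effect: "A significant indirect effect will determine if utilization mediates the relationship between group and outcome". No group-by-utilization term, moderated mediation or separate slope by arm is mentioned.

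The levels of group are not defined for this question. Under Research Question 2, "Utilization data will be collected from participants who use either the app or the chatbot", which points to app versus chatbot. But Section 9 opens with "Three subgroups will be analyzed: the app group, the chatbot group, and the delay group", so a three-level group is not ruled out.

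**The concern.** The two readings do different jobs, and neither fully does the one assigned to it.

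The usage effect is a single coefficient, adjusted for group. Whether the either-group wording means each group or at least one of the two, it is a statement about arm-specific slopes, and the model estimates none. There is reason not to assume a common slope. A visit is counted as any interaction with a feature, and the chatbot is designed to introduce features proactively in a texting narrative, so a visit need not carry the same exposure in the two products.

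The indirect effect combines the difference in use between groups with the use slope. It does not test whether heavier users within a product reduce their drinking more. Hypothesis 3 is worded as mediation, so a null indirect effect could be taken as evidence against its dose-response clause when that clause is true.

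At stake is whether a relation present in one product is credited to both, or a relation present in both is missed because it runs in opposite directions.

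**Working it through.** **Inputs.** The target is a minimum of 50 participants per arm (Section 6, Target Sample Size). The analysis set is completers of both surveys (Section 9), so the analysed number may differ. The documents give no alpha, power, SD or effect size for this question, so there is no stated figure to reproduce. Assumed below: two-sided alpha 0.05, 50 analysed per arm, and a range of slopes.

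**Step 1: the indirect effect.** With G = app or chatbot, M = utilization and Y = change in drinking:

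- M = i + a·G + error
- Y = j + c·G + b·M + error
- indirect effect = a × b

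If mean use is equal, a = 0 and the product is 0 for any b.

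**Step 2: the pooled slope.** Without an arm-by-use term, b is the average of the two arm slopes, weighted by each arm's within-arm sum of squares of use. With equal numbers and equal spread, b = (b_app + b_chatbot)/2. Slopes of 0 and 0.4 give 0.2; slopes of +0.5 and −0.5 give 0.

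**Step 3: simulation.** 2,000 trials per row, 50 per arm, use and residual each with SD 1, Monte Carlo 95% interval for a × b. Negative slopes mean more use goes with more reduction. Entries are the percentage of trials significant.

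| Use difference (SD) | App slope | Chatbot slope | Pooled slope | Indirect effect | App alone | Chatbot alone | Interaction |
|---|---|---|---|---|---|---|---|
| 0 | −0.5 | −0.5 | 99.6 | 4.3 | 90.9 | 92.1 | 5.1 |
| 0 | −0.3 | −0.3 | 82.7 | 4.3 | 53.5 | 52.3 | 4.7 |
| 0.5 | −0.5 | −0.5 | 99.8 | 67.4 | 91.5 | 91.9 | 5.9 |
| 0 | 0 | −0.6 | 79.4 | 3.7 | 5.3 | 98.2 | 82.2 |
| 0 | 0 | −0.8 | 93.7 | 4.4 | 5.3 | 99.8 | 96.3 |
| 0 | +0.5 | −0.5 | 6.6 | 0.2 | 91.6 | 90.8 | 99.6 |

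Rows 1 and 2: the dose-response is real and the planned pooled slope finds it, while the indirect effect does not. Rows 4 and 5: the pooled slope is usually significant although the app has no relation. Row 6: the pooled slope vanishes although both arms have one.

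**Step 4: check by Fisher z**, with slopes expressed as correlations. Power = Φ(√(n − 3)·atanh(r) − 1.960).

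- 0.4 in both arms, pooled, n = 100: 0.4236 × 9.849 = 4.172; less 1.960 = 2.212; power about 99%.
- 0.4 and 0, pooled r = 0.2, n = 100: 0.2027 × 9.849 = 1.997; less 1.960 = 0.037; power about 51%.
- One arm at 0.4, n = 50: 0.4236 × 6.856 = 2.904; less 1.960 = 0.944; power about 83%.
- Difference between 0.4 and 0: 0.4236/√(2/47) = 0.4236/0.2063 = 2.054; less 1.960 = 0.094; power about 54%.

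**Step 5: the coding of group.** If the delay arm is included with use set to zero, and the app and chatbot each average 1.5 SD of use with slope −0.5, the indirect effect against delay is 1.5 × −0.5 = −0.75 (simulated mean −0.76, detected in 100% of 1,000 trials), although the two products are used equally. Delay then has no variation in use, so with group in the model the slope still comes only from the pooled app and chatbot arms. Zero use is itself doubtful: Section 4 gives the wait-list arm the app after 3 months, and Section 7 places follow-up at 4 months.

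**Step 6: the scale of use.** If one unit of use has effect β in both products, standardizing within arm turns the slopes into β × SD_app and β × SD_chatbot. Unequal spread then produces an interaction that is absent in natural units.

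**The case against.** A reader might infer that the plan does not test Hypothesis 3 at all, or that a true Hypothesis 3 would usually be reported as unsupported. The documents do not support this. Section 9 reads the usage effect separately from the indirect effect, and the usage effect is a test of the dose-response clause averaged over the arms. When the slope is 0.4 in both products it has about 99% power, against about 83% for one arm alone. For the common-slope case the planned test is the better one. The indirect effect is reserved for whether use explains the group-outcome relation, which is a legitimate question, and "Participants in the bot group will utilize the intervention significantly more than the app group due to the intervention's conversational interface" shows that the plan expects a difference in use.

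A reader might also infer that the indirect effect is simply zero under equal use. That holds only if group means app versus chatbot. This is the likelier reading, but it is not stated, and it fails if delay enters at zero use.

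Nor do the documents support saying that the next trial would be misdirected. Aim 3 ties that choice to clear superiority or to the effect size between groups, not to Research Question 3.

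Finally, a by-arm analysis is no cure for small numbers. The interaction would miss a contrast of 0.4 versus 0 nearly half the time.

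All of this stands, and it limits the point. It does not rescue the sentence that reads one pooled slope as informative about either group.

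**Conclusion.** The point holds in a limited form. The planned usage effect tests Hypothesis 3's dose-response clause only as an average slope over the app and chatbot arms, so it cannot support a statement about either product. In the assumed examples it is significant in about 51% of trials (slopes 0.4 and 0) to 94% (0 and −0.8) when only the chatbot has a relation, and in 6.6% when the slopes are +0.5 and −0.5. The indirect effect, for app versus chatbot, addresses a different question, and its interval excludes zero in about 4% of trials when use is equal and the dose-response is real.

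These sizes rest on assumed slopes, 50 analysed per arm and alpha 0.05, none of which the plan sets for this question. The algebra does not depend on them. Utilization is not randomized, so every slope here is an association, under the current plan or the revised one.

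**What to change.** In Section 9, Research Question 3:

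- Define group as app versus chatbot only, because the delay arm receives the app before the 4-month follow-up.
- Regress change in drinking on arm, utilization and arm × utilization. Keep utilization in natural units or on one scale common to both arms, not standardized within arm.
- Report each arm's slope with a 95% CI, the pooled slope, and the interaction with its CI. State that significance in one arm only will not be taken as a difference between products.
- Restrict the indirect effect to whether use explains a chatbot-app difference in drinking change.
- Rewrite the either-group sentence to match, and describe the slopes as associations.

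The cost is a paragraph and one extra model term, with no new data. The downside is precision: arm slopes rest on about 50 people each, and the interaction has only about 54% power for slopes of 0.4 versus 0. The slopes and their intervals should therefore lead, with the interaction test in support.
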